Depression and anxiety heighten musculoskeletal pain and negatively impact outcomes after orthopedic surgery. This phenomenon is especially prevalent in older adults. Our ongoing pilot work demonstrates promise that an established digital mental health intervention (Wysa) can improve orthopedic patients' mental health symptoms, but we also encountered implementation barriers related to discussing mental health in an orthopedic setting. The long-term goal of this line of research is to enable the provision of true comprehensive care to improve both the physical and mental health of orthopedic patients. The goals of this project are to address the implementation barriers we encountered in our ongoing pilot work and to prepare for a definitive trial to assess the effectiveness of a digital mental health intervention in the context of orthopedic care.

The specific aims are to:

- 1.) identify the contextual determinants of implementation success for addressing patients' mental health in the context of orthopedic care ;
- 2.) conduct usability testing for two mental health interventions which can feasibly be implemented in a real-world orthopedic setting: a digital mental health intervention (Wysa) and a novel printed resource guide; and
- 3.) identify the intermediate mechanisms through which a digital mental health intervention (Wysa) improves mental health symptoms in orthopedic patients. Using standard qualitative methods and guided by the Consolidated Framework for Implementation Research (CFIR) and the COM-B model of behavior change, two stakeholder groups will be interviewed: orthopedic providers and older adult orthopedic spine patients.

In addition to addressing specific needs and preferences related to discussing mental health in the setting of orthopedic care, patient stakeholders will complete usability testing of Wysa and of the novel printed guide of local and online mental health resources.

Next, the patient stakeholders will receive one month of access to Wysa. They will complete measures of clinical effectiveness (self-reported depression, anxiety, pain interference, physical function) and hypothesized behavioral targets (behavioral activation, pain acceptance, sleep quality) at baseline and one-month

follow-up. The study findings will facilitate design of a subsequent clinical effectiveness trial that is designed for equitable dissemination and effective implementation of mental health intervention within the context of orthopedic care.

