A2 Primary Hypothesis

The expected results of this project are:

- 1.) identification of stakeholder-informed implementation strategies for mental health interventions tailored for the orthopedic setting,
- 2.) refined digital and printed mental health interventions that are scalable and acceptable to older patients, and
- 3.) requisite planning data to facilitate successful completion of a subsequent clinical trial.

A3 Purpose of the Study Protocol

The goals of this project are to:

- 1.) identify effective implementation strategies to introduce mental health intervention in the context of real-world orthopedic care,
- 2.) optimize the usability of two mental health interventions (Wysa and a novel printed resource guide) for older adult orthopedic patients, and
- 3.) identify the intermediate mechanisms through which Wysa has an effect.

B Background

B1 Prior Literature and Studies

Depression and anxiety heighten musculoskeletal pain and negatively impact outcomes after orthopedic surgery.¹⁻⁵ Targeted mental health treatment can improve both physical and mental health in these patients,⁶⁻⁸ but a gap remains in effectively and routinely engaging orthopedic patients in mental health care in an acceptable, sustainable, and scalable fashion. Barriers include: 1.) limited orthopedic provider time and knowledge to discuss mental health resources,⁹ 2.) patient concerns regarding cost, transportation, and time necessary for mental health treatment,¹⁰⁻¹³ and 3.) a national shortage of mental health professionals.¹⁴ These barriers disproportionately affect minority groups of all types.¹⁵

Our ongoing, funded pilot work suggests that an established digital mental health intervention (Wysa) based on behavioral activation, mindfulness, and sleep health meaningfully improves PROMIS Depression and Anxiety scores in orthopedic patients across the adult age spectrum at one- and two-month follow-up. However, the clinical context (e.g., team member leading the discussion, words used to discuss mental

health, volume of information already discussed during the encounter) influences providers' likelihood of discussing the intervention and patients' interest in trying it.

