Depression and anxiety worsen musculoskeletal pain and reduce the effectiveness of traditional orthopedic treatments. Nevertheless, addressing mental health is not currently a part of standard treatment for orthopedic conditions. The purpose of this study is to identify strategies to address mental health in the context of orthopedic care in a manner that is feasible, effective, and acceptable to patients and clinicians.

C Study Objectives

C1 Primary Aim

Aim 1: Identify the contextual determinants of implementation success for addressing patients' mental health in the context of orthopedic care.

Using standard qualitative methods, two stakeholder groups will be interviewed: WU orthopedic providers and orthopedic spine patients ≥ 18 years old, with a focus on patients 65 years and older. Using purposive sampling, a goal of at least half of patient stakeholders will be women, and one quarter will identify as an under-represented minority. In semi-structured interviews guided by the Consolidated Framework for Implementation Research (CFIR) and the COM-B model of behavior change, providers and patients will describe needs and preferences related to addressing mental health in a clinical and research context (e.g., recruiting and retaining orthopedic patients in a mental health related randomized controlled trial).

Aim 2: Conduct usability testing for two mental health interventions which can feasibly be implemented in a real-world orthopedic setting: a digital mental health intervention (Wysa) and a novel printed resource guide.

Using semi-structured interviews and the System Usability Scale (SUS), orthopedic patients will participate in an iterative user design process to refine the delivery of Wysa and a printed guide of local and online mental health resources. The printed guide is being prepared as an “enhanced usual care” control intervention for a subsequent R01 randomized controlled trial proposal.^{17,18}

Aim 3: Identify the intermediate mechanisms through which a digital mental health intervention (Wysa) improves mental health symptoms in orthopedic patients.

In a pilot prospective cohort study, patients will receive one month of access to Wysa. Measures of clinical effectiveness (self-reported PROMIS Depression, Anxiety, Pain Interference, and Physical Function¹⁹) and hypothesized behavioral targets (Behavioral Activation for Depression Scale-SF, Chronic Pain Acceptance

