Questionnaire-8, and Athens Insomnia Scale) will be collected at baseline and one-month follow-up.²⁰⁻²⁶

C2 Rationale for the Selection of Outcome Measures

Depression and anxiety can worsen musculoskeletal pain and reduce the effectiveness of traditional orthopedic treatments. Nevertheless, addressing mental health is not currently a part of standard treatment for orthopedic conditions. The purpose of this study is to identify strategies to address mental health in the context of orthopedic care in a manner that is feasible, effective, and acceptable to patients and clinicians.

D Study Design

D1 Overview or Design Summary

This study will utilize qualitative cross-sectional and quantitative longitudinal methods. In semi-structured interviews, orthopedic providers and patients with spine conditions will discuss their overall perspectives, specific needs, and preferred solutions to addressing mental health impairment in the context of orthopedic care and research. In these sessions, patient stakeholders will also user test two specific mental health interventions: a customized version of a commercial digital mental health intervention (Wysa) and a prototype of a print-based mental health resource guide. The patient stakeholders will be provided one month of Wysa access, and they will complete baseline and follow-up measures related to usability, clinical effectiveness, and intermediate behavioral mechanisms through which Wysa is hypothesized to act. Wysa usage data will be obtained from the app company. Delivery of Wysa and the printed resource guide will be iteratively refined based on user feedback.^{13,29,34-42}

D2 Subject Selection and Withdrawal

Inclusion Criteria

- WU Orthopedics patients who are presenting to a spine specialist for neck and/or back pain (spine surgeon, physiatrist, or APP within either of those two divisions) for new or return evaluation
- 18+ years old
- Musculoskeletal pain for 3+ months

Exclusion Criteria

- Routine post-op visit, with no plans for further surgery at this time
- Endorses mental health crisis (active suicidal or homicidal ideation, psychosis)
- Cognitive impairment which would interfere with meaningful engagement with research interview, questionnaires, and/or intervention

2.a Subject Recruitment Plans and Consent Process

Providers:

- Eligible providers are already known, through departmental contacts

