Interviews will be audio recorded and professionally transcribed. Using inductive and deductive coding approaches based on CFIR and COM-B, a codebook will be developed by one team member, and one or more team members will code all transcripts using NVivo. Group discussion among the research team will be used to resolve coding discrepancies, confirm data saturation has been reached, and organize codes into themes. Scores on the System Usability Scale will be used to iteratively refine both mental health interventions under investigation. Longitudinal PROMIS score changes will be compared between “high” and “low” Wysa users (defined by total Wysa interactions), and associations between changes in behavioral targets (behavioral activation, pain acceptance, sleep quality) and clinical outcomes (depression, anxiety) will be assessed.

G Data Handling and Record Keeping

G1 Confidentiality and Security

Plans to protect the privacy interests of the participants during the conduct of the study:

- 1) Only the minimum necessary private information is collected for the purposes of the study
- 2) Any procedures or interventions conducted as part of the study will be conducted in private setting to the extent possible
- 3) Recruitment/consent will occur in a private setting
- 4) Participants will be able to ask questions in a private setting

Project uses paper and hard copy consents, surveys, data collection forms, research subject binders, or other hard copy materials:

- 1) All materials are stored in secured environment
- 2) Access is limited to research team members only
- 3) Transported securely/shipped with tracking mechanism

Project collects, stores and/or transmits electronic data on mobile devices, desktop computers, servers including cloud servers, email, or any other information in electronic form:

- 1) Password protected
- 2) Access is limited to research team only
- 3) Data in Redcap
- 4) Data in Box
- 5) eCRF system
- 6) Transmitted using recognized security for electronic submission
- 7) Recordings taken during interviews with providers and patients will be reviewed by a study team member, and all personal identifiers will be removed prior to being uploaded into Rev.com to be transcribed into text for qualitative analysis.
- Other

G2 Training

Study coordinator was trained in the Wysa software, and is able to explore the app with the participants in the patient population for use on their own. No formal training is necessary for this study.

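### F3 plans no analysis of Wysa use against change in BADS-SF, CPAQ-8 or AIS, so the Aim 3 analyses alone cannot tie any behavioral target to Wysa

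*Combined protocol and SAP*

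**What the plan says.** C1 states Aim 3 as: "Identify the intermediate mechanisms through which a digital mental health intervention (Wysa) improves mental health symptoms in orthopedic patients". The specific aims in the opening summary use the same wording, and A3 item 3 repeats the purpose as "identify the intermediate mechanisms through which Wysa has an effect". D1 describes the behavioral targets as "intermediate behavioral mechanisms through which Wysa is hypothesized to act".

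C1 lists the measures in two groups. One is "Measures of clinical effectiveness (self-reported PROMIS Depression, Anxiety, Pain Interference, and Physical Function". The other is the hypothesized targets: BADS-SF, CPAQ-8 and the Athens Insomnia Scale (AIS). The events chart in E3 shows all three target scales at baseline and at one month. D1 adds that "Wysa usage data will be obtained from the app company".

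F3 then gives two analyses that bear on Aim 3. The first compares PROMIS change between high and low "Wysa users (defined by total Wysa interactions"). In the second, "associations between changes in behavioral targets (behavioral activation, pain acceptance, sleep quality) and clinical outcomes (depression, anxiety) will be assessed". F3 gives no cut-point for high and low use, no stated summary of change in the targets, and no exploratory label.

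**The concern.** A claim that Wysa works through a target has two parts: Wysa moves the target, and the target moves the symptom. F3 addresses the second part, and it addresses the overall relation of use to symptoms. The first part is not analysed.

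This matters because of the design. Section 2.b states that there is no randomization and no control group, and 2.e states that patients carry on with their orthopedic care. Sleep, activity, pain acceptance and mood may improve together for reasons unrelated to the app. A correlation between target change and mood change is then expected whether or not Wysa changed the target. Variation in use is the only between-patient contrast in exposure that the study has, and F3 does not apply it to the targets.

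At stake is what Aim 3 can report. Followed as written, the plan would show which targets move with mood, with no planned estimate of whether any of them moves with Wysa use.

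**Working it through.** **No plan figure to reproduce.** F1 reports no power calculation and sets the sample size by interview saturation. F3 gives no alpha, effect size or SD. The check is therefore mainly textual, and every n and r below is an assumption.

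**Step 1: set the links side by side.**

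| Link | Planned in F3? | Data collected? |
|---|---|---|
| Use to symptom | Yes: PROMIS change, high vs low users | Yes (D1, E3) |
| Target to symptom | Yes: 3 targets x 2 outcomes = 6 pairs | Yes (E3) |
| Use to target | No: 0 of 3 | Yes (D1, E3) |

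The PROMIS comparison cannot be read as covering the targets, because C1 lists PROMIS as four domains and lists the targets separately. No other section that mentions Aim 3, Wysa usage or the three scales supplies the missing analysis.

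**Step 2: do the two planned links imply the third?** For use U, target change T and symptom change S, the possible correlations between U and T are

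r(UT) = r(US) x r(TS) ± sqrt[(1 - r(US)²)(1 - r(TS)²)].

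Assume r(US) = 0.2 and r(TS) = 0.5. Then r(UT) = 0.10 ± sqrt(0.96 x 0.75) = 0.10 ± 0.85, or about -0.75 to 0.95. Zero and substantial positive values are both compatible with identical results from the planned analyses.

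A simulation with the same inputs shows this at n = 30 (20,000 normal datasets per setting, median split for high/low use):

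| True r(UT) | Mean target-symptom r | Mean high-low symptom difference | Mean use-target r (2.5th to 97.5th percentile) |
|---|---|---|---|
| 0 | 0.49 | about 0.31 SD | 0.00 (-0.36 to 0.36) |
| 0.2 | 0.49 | about 0.31 SD | 0.20 (-0.17 to 0.53) |
| 0.3 | 0.49 | about 0.31 SD | 0.29 (-0.06 to 0.60) |
| 0.4 | 0.49 | about 0.31 SD | 0.39 (0.05 to 0.67) |

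The constancy of the two middle columns follows from the inputs. It illustrates the logic and does not measure a harm. The ranges in the last column overlap, so the added estimate would be informative but imprecise.

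**Step 3: precision of the missing estimate.** The 95% interval for a correlation is tanh[atanh(r) ± 1.96/sqrt(n - 3)]. For r = 0.4 and n = 30: 0.424 ± 1.96/sqrt(27) = 0.424 ± 0.377, which transforms back to 0.05 to 0.66.

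| Observed r | n = 20 | n = 30 | n = 40 |
|---|---|---|---|
| 0.2 | -0.27 to 0.59 | -0.17 to 0.52 | -0.12 to 0.48 |
| 0.3 | -0.16 to 0.66 | -0.07 to 0.60 | -0.01 to 0.56 |
| 0.4 | -0.05 to 0.72 | 0.05 to 0.66 | 0.10 to 0.63 |

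With equal high and low groups, the half-width for a difference in a target is t(0.975, n - 2) x sqrt(4/n) SD. At n = 30 this is 2.048 x 0.365 = 0.75 SD (0.94 at n = 20, 0.64 at n = 40). For the mean change in the whole cohort it is t(0.975, n - 1)/sqrt(n) SD of change. At n = 30 this is 2.045/5.477 = 0.37 (0.47 at n = 20, 0.32 at n = 40). These figures are unadjusted, and a baseline-adjusted estimate will have somewhat different precision.

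**The case against.** The strongest reply is that this is a small pilot whose primary aim is qualitative. C1 calls Aim 3 a pilot cohort, and C1 and D1 call the targets and mechanisms hypothesized. The missing estimate would be exploratory, and it can be added later from data already in hand. This largely stands. It limits the size of the point, but it does not supply the analysis. The aim still says identify, F3 carries no exploratory label, and an analysis added later would not have been chosen before the results were seen.

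A second reply is that the added link shares the weakness of the planned ones. Under 2.e patients decide how much to use the app, so motivation and symptom course confound any relation of use to target. A null would not rule out a mechanism either, since a patient who improves may stop using the app. This stands in full, and the added estimate must be presented accordingly. F3 already accepts the same limitation for PROMIS.

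A third reply is that F3 already needs target changes, so reporting their mean is only presentation. That is fair for the mean change. It does not apply to the relation with use.

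A fourth reply is that a baseline-adjusted one-month score sits awkwardly beside F3's change scores. This is minor: once baseline is in the model, the use coefficient is the same whether the outcome is the one-month score or the change.

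**Conclusion.** The gap is real and worth fixing. F3 plans none of the three use-to-target estimates, and its two planned analyses cannot on their own connect a target to Wysa. This conclusion rests on the text. The correlations and sample sizes above are assumed and serve only to show the logic and the likely precision.

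Three stronger readings are tempting, and the documents do not support them.

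- A reader might infer that wrongly chosen targets will be carried into the later randomized trial. The opening summary says only that the findings will facilitate that trial's design, A2 expects planning data, and no rule selects or drops targets on these results.
- A reader might infer that adding the link would establish mediation. With self-selected use, no control group and two time points, it can suggest candidate mechanisms only.
- A reader might take the high/low grouping as already defined and ready to reuse. F3 gives the metric but no cut-point.

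**What to change.** Add to F3, for each of BADS-SF, CPAQ-8 and AIS:

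- the mean baseline-to-one-month change with a 95% CI, labelled descriptive because there is no control group;
- a regression of the one-month score on total Wysa interactions, adjusted for that scale's baseline and checked for skew and influential heavy users, reported with a 95% CI and no significance gate.

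If the high/low grouping is preferred, state its cut-point (for example the median) before the target data are analysed, and use the same cut-point for the PROMIS comparison.

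Label the Aim 3 analyses exploratory. State that self-selected use, the absence of a control group and only two time points mean that they can suggest mechanisms but not establish them.

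The cost is three change estimates and three use-to-target estimates on data already collected, with no effect on enrolment or visits. Intervals will be wide and confounding remains. Total interactions also pool features that may not bear on a given target, although 2.e indicates that use of each feature is received. The aim will read less strongly than it does now.
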